6. STUDY DESIGN SUMMARY

6.1 Summary of Trial Design

This study will employ both qualitative and quantitative measures in order to evaluate the resources required to implement routine lung function testing for children in primary care; and to investigate the impact this would have on diagnosis in children with suspected or presumed asthma. In total we hope to recruit between 3-6 GP sites across Leicestershire and Northamptonshire for the study, which would represent a patient population of ~120,000-150,000 people, representing 1500-2000 children potentially eligible to take part in the study based on our preliminary data. Primary care sites will be approached by the study team with assistance from the CCG R+D manager for Leicester ([name]) and the CRN locality manager for East Midlands ([name]). We aim to recruit sites of differing sizes and with different patient demographics.

Site survey questionnaires will be completed for each site by the study team to gather information about the individual practice's patient population and current asthma review set up. Readiness for change questionnaires will be used to investigate staff opinions, concerns and perceived barriers to implementation. These will be sent out to GPs, practice nurses, HCAs and practice managers at each participating site. The study team will develop and refine a package of training and support which will be based on an existing training programme for primary care practitioners to perform spirometry on adult patients with COPD in Leicestershire primary care practices. We will evaluate the success of the training by supporting and monitoring the primary care practitioners utilising these tests in primary care asthma review clinics. The length of training required in order for different staff groups to be able to perform spirometry and FeNO testing independently will be documented.

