8.2 Screening and Eligibility Assessment

Children who clinically warrant an asthma review, which are also our potential participants, will be identified by the direct care team from participating GP sites. The direct care team will search their practice electronic database for children who meet the inclusion criteria using age limits "5 to 16 years," and to include children who are either on the asthma register or based on asthma medications prescribed as detailed in the inclusion criteria above.

Once identified, the direct care team will send by post the standardised PIS along with the asthma review invitation letters to families. The invitation letter will invite families to phone the GP practice to book onto an asthma review clinic. We anticipate that there will be a minimum of 1 week between the time families receive PIS and the next available asthma review clinic.

Demographics

The date of birth, gender, race, primary language and country of birth will be recorded by the research team in the CRF following written consent at the asthma review.

Medical History

Details of length of asthma diagnosis or duration of “asthma” symptoms will be recorded at time of asthma review by study team following written consent along with concomitant medication and any physical examination (detailed below).

Concomitant Medication

All prescription “asthma” medications (bronchodilators, inhaled steroids, leukotriene receptor antagonists etc.) will be recorded on CRFs and assigned to a corresponding asthma treatment step as detailed in BTS/SIGN asthma guidelines. We will also record number of days of oral steroids prescribed in the preceding 6 months.

Physical Examination

Height and weight of participating children will be recorded.

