8.3 Baseline Assessments

Health Care Workers’ Training Needs

The study team will gather information using site survey and readiness for change questionnaires at each participating practice. It is expected that practice GPs, nurses, HCAs and managers will complete these questionnaires.

The study team will seek the views particularly, but not exclusively, of the healthcare workers performing the objective tests (spirometry and FeNO) on the delivery and content of the training package and the training time available to those performing the tests.

Assessments Performed as Part of Recommended Standard Asthma Review

Asthma control test: We will use validated asthma control tests for children 4 to 11 years (7 questions) (17) and children 12 years and older (5 questions).

Check inhaler technique: Inhaler technique will be checked by the PN/HCA following training if required. An instruction sheet with written information and pictures will be given to the family.

Check prescription record: We will check and document the electronic prescribing record and dispensing record where available for asthma medication in the previous 6 months including the number of reliever and preventer inhalers. As part of the asthma review the practice PN/HCA will also check the prescription records and inform the GP if they have concerns regarding: suboptimal asthma control; where reliever and preventer medication use are unbalanced for example in cases where preventer prescribing is low and reliever prescriptions are high; and where there are concerns regarding adherence (i.e. fewer than expected number of inhalers dispensed).

Any child presenting to the review visit unwell or with poor lung function (FEV1 <75% predicted) will be referred to the practice GP for assessment.

Written personalised asthma action plan: All children will be given a written personalised asthma action plan. Where children already have an action plan this will be reviewed.

Spirometry and FeNO testing: Children will be asked to perform spirometry and a FeNO measurement where indicated.

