8.5 Subsequent Assessments

We will have only one face to face contact with each study participant throughout the study. Having taken appropriate consent, we will review each participants electronic record 3-6 months following the initial asthma review to record any changes in prescription patterns, additional primary care review for exacerbations or hospital attendances. In patients who have agreed, we will also send out a follow up postal health economic questionnaire and asthma control test 3-6 months following the review.

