11. STATISTICS

11.1 Description of Statistical Methods

The qualitative data regarding opinions and barriers to implementation derived from change questionnaires conducted with the participating GP practices will be presented in report form. Appropriate non-parametric tests such as Kruskal-Wallis, Wilcoxon paired signed and Friedmans 2-Way ANOVA will be used to assess data; including the changes in number of children diagnosed with asthma, the number of misdiagnoses and alterations in prescribing (number of salbutamol inhalers/steroid courses) as a result of implementation of objective lung function tests. Paired t-tests or paired Wilcoxon signed rank tests will be used to assess the change in asthma control test scores, number of school days missed and number of carer work days missed.

A generalized linear mixed model with logit link function will also be used to compare the proportion of children with a personalised asthma plan and other secondary outcomes. The models will include important covariates such as age, gender and ethnicity, and the clustering effect of GP clinic will be accounted for. The effect of GP clinic will also be assessed by fitting a mixed effects model, GP clinic will be fitted as a random effect, covariates such as age, gender and ethnicity will be fitted as fixed effects.

All statistical analysis will be performed using R 3.2.0 (<http://www.r-project.org/>) and SPSS v22.

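### Section 11.1 names no baseline severity measure as a covariate, so in models of follow-up outcomes a difference in starting severity between clinics can appear as a clinic effect

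*Combined protocol and SAP*

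**What the plan says.** Section 11.1 describes two regression analyses. The first is for binary secondary outcomes: "A generalized linear mixed model with logit link function will also be used to compare the proportion of children with a personalised asthma plan", together with other secondary outcomes that are not listed. Of its covariates it says "The models will include important covariates such as age, gender and ethnicity". The second assesses the effect of the practice itself: "GP clinic will be fitted as a random effect, covariates such as age, gender and ethnicity will be fitted as fixed effects". No outcome or link function is given for this second model. Change in asthma control score, school days missed and carer work days missed go to paired tests, outside these models.

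Several measures of starting severity are recorded at the review:

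- **Asthma control** (8.3): "We will use validated asthma control tests for children 4 to 11 years", with a separate instrument from age 12.
- **Oral steroids** (8.2): "We will also record number of days of oral steroids prescribed in the preceding 6 months".
- **Inhalers** (8.3): numbers of relievers and preventers over the previous 6 months.
- **Treatment step** (8.2): medication is "assigned to a corresponding asthma treatment step as detailed in BTS/SIGN asthma guidelines".

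Follow-up consists of a record review and, for families who agree, an "asthma control test 3-6 months following the review" (8.5). On the choice of practices, 6.1 says "We aim to recruit sites of differing sizes and with different patient demographics". No section names any of the severity measures as a covariate.

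**The concern.** Clinic is more than a nuisance term here, because 11.1 says its effect will be assessed. Where an outcome is measured after the review and depends on how ill the child was at the review, a clinic that starts with sicker children will tend to have worse follow-up values. Age, gender and ethnicity remove only the part of that difference that they happen to explain. The rest stays in the clinic term and could be read as a difference in how well practices carried out the new testing.

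The open list adds a second problem. Whether a clinic effect appears can depend on which covariates go in, and 11.1 leaves that choice until after the data are seen. Section 11.6 promises to report deviations from the plan, but an open list gives little to deviate from.

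**Working it through.** **The plan's own figure.** The target of 1000 children (11.2) comes from feasibility. The eligible pool is 1500-2000 (6.1) and the recruitment rate 50-70%: 1500 × 0.5 = 750 and 2000 × 0.7 = 1400. The target lies inside that range, and 2000 × 0.5 = 1000 exactly. The plan gives no effect size, correlation or between-clinic spread, so **every severity input below is an assumption**.

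**Check 1: logit model.** 1000 children, 3 or 6 clinics (6.1 allows 3-6), no true clinic effect, one standardised severity score with an odds ratio of 1.5 or 2.0 per SD, one other covariate, 400 runs per setting. The clinic test is a 5% likelihood ratio test with clinic as a fixed factor, standing in for the random effect.

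| Share of severity variance between clinics | Clinic test significant, severity omitted | Severity included |
|---|---|---|
| 0% | 4.5-6.5% | 5.0-8.7% |
| 1% | 5.0-8.5% | 4.5-6.0% |
| 5% | 16-30% | 5-6.5% |
| 10% | 22-57% | 5-6% |

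The Monte Carlo standard error near 5% is √(0.05 × 0.95/400) = 1.1 points. The 8.7% is one cell with no case-mix difference at all, so I read it as simulation noise. At 8.5% the standard error is √(0.085 × 0.915/400) = 1.4 points, so the 1% row could reach about 8.5 + 2 × 1.4 = 11.3%.

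**Check 2: which analysis removes the problem.** This uses a continuous outcome because the change score can then be compared directly. Assumptions: 1000 children, 6 equal clinics, baseline-to-follow-up correlation ρ = 0.5, between-clinic SD of baseline τ = 0.1, 0.2 or 0.3 child-level SD. As variance shares, τ²/(1 + τ²), these are about 1%, 4% and 8%. Two situations were simulated, neither with a real difference in clinic performance.

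*Common mean:* all children regress to one mean. The clinic SD is ρτ in the follow-up value and (1 − ρ)τ in the change.

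*Stable clinics:* children regress to their own clinic's mean, and no clinic changes.

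| Clinic test significant at τ = 0.1 / 0.2 / 0.3 | Follow-up value, no baseline | Change score | Follow-up value, baseline included |
|---|---|---|---|
| Common mean | 17 / 53 / 82% | 16 / 52 / 81% | 4-6% |
| Stable clinics | 53 / 91 / 98% | about 5-7% | 21 / 58 / 85% |

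A closed form confirms the first cell. With n = 1000/6 = 166.7 per clinic, residual variance 1 and clinic SD δ = ρτ, the rejection rate is P(F(5, 994) > 2.22/(1 + nδ²)). For δ = 0.05, 0.10 and 0.15, 1 + nδ² is 1.42, 2.67 and 4.75, giving 17%, 53% and 80%.

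Including baseline beats omitting it in both situations. The change score fails in the first and holds its level in the second.

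**Check 3: what adjustment cannot cure.** Ignoring within-clinic error, a 95% interval for the between-clinic SD runs from √((K − 1)/χ²(0.975)) to √((K − 1)/χ²(0.025)) times the estimate. For K = 3 this is √(2/7.38) = 0.52 to √(2/0.0506) = 6.3. For K = 6 it is √(5/12.83) = 0.62 to √(5/0.831) = 2.5.

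**The case against.** **The list is open.** This stands. The covariates are given as examples, so a reader might infer that 11.1 excludes severity, and it does not. The defect is that no severity measure is named.

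**Precision.** A reader might infer that leaving out a strong predictor also costs precision. For the logit models the simulation does not support this: the standard error of another covariate was 0.065-0.066 without severity and 0.067-0.069 with it. Omission instead pulled that coefficient towards zero (0.27-0.29 against a true 0.30). A precision gain belongs to continuous outcomes, and the plan names none for these models.

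**Change scores.** A reader might conclude that change should not be analysed. Check 2 does not support that. With non-randomised clinics, neither baseline adjustment nor change is known to be unbiased.

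**Over-adjustment.** Treatment step and prior prescribing partly reflect each practice's own habits, so adjusting for them may remove part of a real clinic difference. This stands, and it is why treatment step belongs in a sensitivity analysis.

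**Relevance.** No objective in section 5 compares clinics, and the one outcome that 11.1 names, the personalised plan, is to be given to all children (8.3). Both points stand and limit the weight of the concern. But 11.1 still commits to assessing a clinic effect.

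**Severity may not differ.** Section 6.1 speaks of differing size and demographics, and the models already include demographics. That severity differs beyond this is an inference with no figure behind it.

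**Conclusion.** The concern holds in a limited form. If follow-up outcomes are modelled with only the covariates that 11.1 names, case-mix can be read as a clinic effect. The size is unknown. In a logit model it is small if about 1% or less of severity variance lies between clinics after demographics, and material at 5-10%. These figures rest on assumed odds ratios, correlation and spread, and on a fixed-effect clinic test in place of the random-effect one.

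Adding the baseline value improves on leaving it out in both situations examined, but does not guarantee an unbiased clinic comparison. With 3-6 clinics the clinic variance stays imprecise under any covariate set. Only the secondary and clinic-effect analyses are affected, not the primary endpoint.

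**What to change.** Replace the covariate wording in 11.1 with text along these lines:

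> *Each mixed model of a follow-up outcome will include, besides age, gender and ethnicity, the baseline value of that outcome where it is recorded: asthma control test score (entered by age-specific instrument), oral steroid use, or inhaler count. The clinic effect will be reported from this model. Sensitivity analyses will show the clinic effect (a) without the baseline value, (b) on the change score, and (c) with BTS/SIGN treatment step and other prior prescribing added.*

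For (b), steroid and inhaler counts need a common time base, because the look-back is 6 months and follow-up is 3-6 months. The report should say that (c) may remove genuine differences in clinic practice.

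The cost is a few sentences. No new data, visits or staff are needed, and missing baseline values can go through the multiple imputation planned in 11.5, subject to its restrictions. The downsides are a few more parameters and some risk of over-adjustment.

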11.2 The Number of Participants

We plan to recruit 1000 children into the study. This number has been derived from the expected number of children in the participating practices who would meet the inclusion criteria based on epidemiological data and preliminary searches. It also takes into consideration the capacity of the study team, the study length and anticipated recruitment rates of 50-70%.

11.3 The Level of Statistical Significance

All statistical tests will be performed at the alpha=5% level.

11.4 Criteria for the Termination of the Trial.

Once we have accessed the records of the final child to be recruited and they have returned the follow up questionnaire.

11.5 Procedure for Accounting for Missing, Unused, and Spurious Data.

A table listing all key variables with percentage of missing data will be reported and where possible the reason for missing data will be reported. Within the multivariate regression framework missing data will be imputed using multiple imputation. To avoid bias, where it can be reasonably established that data is not missing at random, covariates will not be imputed, a complete case analysis will be used. Outcome variables missing not at random will not be imputed, sensitivity analysis will be performed and an assessment of the models made based on the missing at random assumption. Spurious data will be reported and where possible correct values will be inserted, if it is not possible to supply correct values, value will be deleted.

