11.7 Inclusion in Analysis

We plan to include data from all participants in the analysis.

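### The change in ACT is tested only in children whose postal form comes back, because multiple imputation is confined to the regression models

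*Combined protocol and SAP*

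**What the plan says.** Four parts of the combined protocol and SAP bear on this.

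- **Test (11.1).** "Paired t-tests or paired Wilcoxon signed rank tests will be used to assess the change in asthma control test scores". Numbers of school days and carer work days missed are assigned to the same tests.
- **Source of the follow-up score (8.5).** "In patients who have agreed, we will also send out a follow up postal health economic questionnaire and asthma control test", at 3-6 months. Sections 8.1 and 9.1 agree that it is postal and needs consent. No expected return rate and no reminder procedure is given, and 11.4 presumes that the last family's form comes back.
- **Missing data (11.5).** "Within the multivariate regression framework missing data will be imputed using multiple imputation". The section also promises a table of percentages missing, with reasons where possible. Outcomes judged missing not at random are left unimputed, with a sensitivity analysis whose content is not described.
- **Analysis population (11.7).** "We plan to include data from all participants in the analysis". No analysis set is defined for any outcome.

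Section 8.5 also states "we will review each participants electronic record 3-6 months following the initial asthma review". That review covers prescriptions, primary care visits for exacerbations and hospital attendances. None of it depends on a form being posted back.

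**The concern.** A paired test silently drops any child with one score. The ACT is the documented outcome most exposed to postal non-return, yet the stated missing-data method does not reach the test assigned to it. Whether a family returns a form may depend on how well controlled the child was at the review, or on what happened afterwards. In either case the mean change among returners differs from the mean change among the children recruited.

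A large sample does not protect against this, because it narrows the interval around a biased value. The study has no randomised comparison (8.4) in which the same distortion might show up in another arm. What is at stake is the reported evidence on asthma control after the reviews, not the training and capacity objective.

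**Working it through.** **1. The plan's own number.** "We plan to recruit 1000 children into the study" (11.2). Section 6.1 gives the pool as "representing 1500-2000 children potentially eligible to take part in the study based on our preliminary data", with a recruitment rate of 50-70%.

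- 1500 x 0.50 to 1500 x 0.70 = 750 to 1050
- 2000 x 0.50 to 2000 x 0.70 = 1000 to 1400

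The figure of 1000 lies within these ranges and equals 2000 x 0.50. It is a feasibility number. There is no power calculation and no allowance for forms that do not come back.

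**2. Bias of the complete-pair mean change.** Let r be the return rate, with D1 and D0 the mean change in returners and non-returners. The mean over all children is r x D1 + (1 - r) x D0, so

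bias = D1 - [r x D1 + (1 - r) x D0] = (1 - r) x (D1 - D0).

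This is an identity. The documents give neither r nor D1 - D0, so both are assumed below.

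**3. Illustration.** Assume 1000 children, a true mean change of 0 and a gap D1 - D0 = 0.25 SD of change. Section 11.3 sets the level ("All statistical tests will be performed at the alpha=5% level") without stating sidedness; two-sided is assumed. With b the bias in SD and n = 1000r, the rejection rate is approximately Φ(b√n - 1.96) + Φ(-b√n - 1.96).

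| Assumed return | Pairs used | Bias (SD) | Rejection of a true null |
|---|---|---|---|
| 30% | 300 | 0.70 x 0.25 = 0.175 | 86% |
| 50% | 500 | 0.50 x 0.25 = 0.125 | 80% |
| 70% | 700 | 0.30 x 0.25 = 0.075 | 51% |
| 90% | 900 | 0.10 x 0.25 = 0.025 | 12% |

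Reversing the sign of the gap reverses the bias and leaves the rejection rate unchanged.

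**4. Can data already collected repair it?** A simulation used 1000 children, 2000 runs, true mean change 0 and an assumed correlation of 0.5 between baseline and follow-up. Return depended on baseline only, through a logistic model. At log-odds 0.5 per baseline SD:

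| Assumed return | Complete-pair bias (SD of score) | Rejection of a true null | Bias using baseline for all 1000 (SD) |
|---|---|---|---|
| 30% | -0.166 | 82% | 0.0007 |
| 50% | -0.118 | 76% | -0.0003 |
| 70% | -0.071 | 48% | 0.0006 |

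The mechanism is regression to the mean. When children with higher baseline scores return more often, the pairs show a fall that the whole group did not have. With return unrelated to baseline, complete-pair bias was at most 0.002 SD in absolute value and rejection was 4.5-5.1%. The simulation covers missingness explained by an observed variable. It does not show that imputation would cure missingness that depends on the unseen follow-up score.

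**The case against.** The strongest reply is that 11.5 is not silent. It promises a missingness table and a sensitivity analysis, and it deliberately declines to impute outcomes missing not at random. If return depends on how the child is doing even after conditioning on observed data, that is exactly the case it sets aside. This stands in part: any extension of imputation must be reconciled with that rule. But a table describes the gap without correcting it, and the sensitivity analysis is unspecified and tied to the models rather than the paired tests.

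A second reply is that 11.1 sends unnamed further secondary outcomes to a logit mixed model, and describes a mixed model with clinic as a random effect without naming its outcome. A modelled, imputed ACT analysis is therefore not excluded. That is correct, but it is not stated either. The paired test is the only analysis named for ACT change, and a logit link does not suit a score.

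A third is that ACT change is not among the endpoints in 6.2 or the listed secondary objectives in 5.2. It appears as an impact measure in 9.1. This limits the importance of the point without removing it.

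Four stronger readings are tempting, and the documents do not support them:

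- **That 11.7 is contradicted.** It can be read as using all available data, so this is an unresolved tension.
- **That school and carer work days are postal.** They are absent from the record-review items, so it is a reasonable inference, but no section names their instrument.
- **That 50-70% is the expected return.** In 6.1 and 11.2 that figure concerns recruitment.
- **That the bias must favour improvement.** The formula allows either sign, and zero if return is unrelated to change.

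**Conclusion.** The point holds for ACT. As written, its change is estimated only from children whose form is returned, and the stated imputation does not extend to that test. The same holds for school and carer work days if they are collected on the postal form.

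The bias is conditional and its size cannot be computed from the documents. The 0.175 to 0.025 SD range rests entirely on an assumed 30-90% return and an assumed 0.25 SD gap. It should not be restated in ACT points: no SD is given, and 8.3 uses two versions (7 questions up to age 11, 5 questions from age 12), so a point is not one unit across the sample.

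This is worth correcting before analysis because the plan already uses multiple imputation elsewhere and already collects plausible predictors for every consented child. It does not affect the primary objective.

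**What to change.** In 11.1, 11.5 and 11.7:

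1. State the analysis set for each outcome, and name the instrument and time points for school and carer work days.
2. Analyse ACT change for all consented children by multiple imputation or an equivalent model. Do the same for days missed once their source is named. Use as predictors the baseline score, age, gender, ethnicity, BTS/SIGN treatment step, clinic and the 3-6 month record data (prescriptions, exacerbations, hospital attendances).
3. Handle the two age-specific ACT versions separately.
4. Report the complete-pair test alongside, and tabulate baseline data for returners and non-returners.
5. Specify the missing-not-at-random sensitivity analysis that 11.5 promises, for example a delta shift applied to imputed values. By the identity above, a shift of δ in every imputed change moves the overall mean change by (1 - r) x δ. Reword the rule against imputing such outcomes so that it fits with this analysis.

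The cost is SAP wording and modest extra analysis. No new data are needed beyond settling where days missed are recorded. The result would rely on missing-at-random given the observed data, a weaker assumption than the complete-pair test makes but still untestable. A large share of outcomes may be imputed if return is poor, and 3-6 clinics give little support for a random effect.
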